6.3.2.2. The Alzheimer's Disease Cooperative Study Activities of Daily Living Inventory

The ADCS-ADL measures 6 basic and 17 instrumental activities of daily living and was specifically developed as a sensitive tool to track changes in functional performance in AD over time (Galasko et al 1997, Galasko et al 2004). The basic activities include self-care tasks such as

eating, walking, toileting, bathing, and grooming. The instrumental activities are more complex skills that are required to successfully live independently and include shopping, keeping appointments, traveling outside of home, making a meal or snack, reading, and writing. These instrumental skills are often compromised in early AD.

For each activity on the ADCS-ADL, the score ranges from 0 (not able to perform the activity or needs extensive help) to the highest score (independently performs the activity).

The maximum ADCS-ADL total score is 78, with lower scores indicating greater impairment. The maximum basic items score (sum of individual basic item scores) is 22, and the maximum instrumental items score (sum of individual instrumental item scores) is 56 (Galasko et al 2004).

The ADCS-ADL is a study partner/informant rating, and the administration of the scale takes approximately 15 minutes.

The ADCS-ADL assessment results will be recorded on worksheets. Administration of the ADCS-ADL will be audio-recorded for quality-control and training purposes where permitted by local law. Item-level scores from the worksheet will be transcribed into the eCRF. A sample of the ADCS-ADL worksheets and audio recordings will be centrally reviewed and monitored where permitted by local law. Follow-up with raters will occur if concerns about administration and/or scoring practices are observed in central monitoring.

6.3.2.3. Clinical Dementia Rating Scale

The CDR (Hughes et al. 1982) is a global rating system widely used in clinical studies of AD as a measure of dementia severity and disease progression. The CDR ratings are based on a semi-structured and in-depth interview with both the patient and the patient's study partner. The CDR rates decline in cognition and its impact on functioning relative to the patient's own premorbid ability levels. Although the rater may administer selected cognitive tasks during the interview to further estimate the patient's cognitive and functional abilities, the CDR ratings do not rely directly on psychometric test performance. The interview takes approximately 45 minutes to administer and requires a trained and experienced rater. The CDR rater should, as much as possible, not have access to information regarding AEs.

The CDR includes assessment of 6 independent domains: Memory, Orientation, Judgment and Problem Solving, Community Affairs, Home and Hobbies, and Personal Care. Each independent domain is rated at each assessment time point on a scale from 0 to 3 (0 = none, 0.5 = questionable, 1 = mild, 2 = moderate, 3 = severe). These domain ratings are also known as "box" scores. The Sum of Boxes score is derived by adding the individual box scores at a given time point. The maximum Sum of Boxes score is 18, with higher scores indicating greater impairment. The CDR global score is a composite score calculated using the Washington University CDR-assignment algorithm applied to the 6 individual domain box scores (Morris 1993). The memory domain is considered the primary category that drives the CDR global outcome, and all other domains are secondary. The CDR global score ranges from 0 to 3 (0 = no dementia, 0.5 = questionable dementia, 1 = mild dementia, 2 = moderate dementia, 3 = severe dementia). The CDR global score and memory box score will be used to determine patient

eligibility for the study and categorize patients as having either MCI due to AD or mild AD, as described in Section 4.1, inclusion criteria.

The CDR assessment results will be recorded on worksheets. Administration of the CDR will be audio-recorded for quality-control and training purposes where permitted by local law. The box scores and global scores from the worksheet will be transcribed into the eCRF. A sample of the CDR worksheets and audio recordings will be centrally reviewed and monitored where permitted by local law. Follow-up with raters will occur if concerns about administration and/or scoring practices are observed in central monitoring.

Time in the current disease state will be assessed in terms of time to loss of 1 global stage on the CDR global score through Week 104.

6.3.2.4. Integrated Alzheimer's Disease Rating Scale (iADRS) [calculated assessment, not a separately administered scale]

The iADRS (Wessels et al 2015) is a composite that measures both cognition and function. The iADRS is a simple linear combination of scores from two well-established, therapeutically sensitive, widely accepted measures in AD, the ADAS-Cog₁₃ and the instrumental activities within the ADCS-ADL (ADCS-iADL), measuring the core domains of AD. All items of these two scales are included without additional weighting of items, yielding face validity and ease of interpretation of the composite relative to its components.

The iADRS provides an overall measure of AD impairment (total score) and can also provide individual subscores for cognition and function based on standard, accepted instruments. The iADRS demonstrated acceptable psychometric properties (established through principal component analysis, estimation of the contributions of domain scores to the iADRS total score, and estimation of the contributions of individual item scores to the iADRS total score) and was effective in capturing disease progression and treatment effects (both beneficial and detrimental) across a broad range of the symptomatic disease spectrum – MCI/prodromal, mild AD dementia, and moderate AD dementia populations.

The iADRS score ranges from 0-141; with higher scores indicating greater impairment.

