6.3.1. Primary efficacy variable

Cognitive function will be assessed using a 13-item version of ADAS-Cog. The ADAS-Cog₁₃ measures severity of impairment in various cognitive domains (memory, language, orientation, praxis and executive functioning). The ADAS-Cog has been designed specifically for the evaluation of the severity of major dysfunctions in the cognitive behavior characteristics of patients with AD. It has frequently been used in drug studies in AD of mild-to-moderate severity and is recognized by regulatory authorities. Most item scores are based on the number of words not recalled or the number of errors: Word Recall, Commands, Constructional Praxis, Delayed Word Recall, Naming, Ideational Praxis, Orientation and Word Recognition. Remembering Test Instructions is rated based on the number of reminders during the Word Recognition task. Spoken Language Ability, Comprehension of Spoken Language, and Word-finding Difficulty are rated on a scale of severity of dysfunction ranging from 0 to 5, where 0 = no impairment, 1 = very mild, 2 = mild, 3 = moderate, 4 = moderately severe, and 5 = severe. The score for the Number Cancellation item ranges from 0 to 5, based on ranges of numbers of target items correctly crossed off by the patient within the time limit; the fewer correct responses, the higher the score.

The ADAS-Cog₁₃ is composed of the original 11-item ADAS-Cog (Rosen et al. 1984) as well as Delayed Word Recall and Number Cancellation items. The Number Cancellation task has been shown to be reliable and sensitive to a broad range of dementia severity and, therefore, is a useful addition to the 11-item ADAS-Cog (Mohs et al. 1997). The additional items in ADAS-Cog₁₃ demonstrate good psychometric properties, even in subjects without AD. These items show excellent retest reliability and no ceiling effects observed on Delayed Word Recall and Number Cancellation items (Raghavan 2013; Wessels et al. 2015)

The maximum score for the ADAS-Cog₁₃ is 85 points. A lower score indicates a better performance.

The ADAS-Cog₁₃ word lists and number cancellation will not be the same at consecutive visits, that is, word lists and number cancellation will be alternated and thus vary by visit.

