11.1.6. Mini-mental State Examination

A total score will be computed across all dimensions of the MMSE and used as an outcome variable in the statistical analysis.

Changes from screening MMSE total score at each post-baseline time point will be calculated as the post-baseline score minus the screening score.

11.1.7. iADRS cognitive/functional composite measure

For additional details regarding the iADRS scale see Section 6.3.2.4.

Changes from baseline iADRS total score at each post-baseline time point will be calculated as the post-baseline score minus the baseline score.

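### Does the iADRS definition let cognitive and functional effects cancel, because neither component is said to be reversed?

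*Protocol*

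**What the plan says.** The iADRS is a secondary endpoint at Week 104 and at other time points (Protocol Table 1 in Section 2.2; also Sections 6.3.2 and 12.2.1).

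- **Cognitive component** (Section 6.3.1): "The maximum score for the ADAS-Cog₁₃ is 85 points. A lower score indicates a better performance".
- **Functional component** (Section 6.3.2.2): "The maximum ADCS-ADL total score is 78, with lower scores indicating greater impairment". For the part used in the iADRS, "the maximum instrumental items score (sum of individual instrumental item scores) is 56".
- **Composite** (Section 6.3.2.4): a linear combination of the two scores. On weights: "All items of these two scales are included without additional weighting of items". On range and direction: "The iADRS score ranges from 0-141; with higher scores indicating greater impairment".
- **Derivation** (Section 11.1.7): "For additional details regarding the iADRS scale see Section 6.3.2.4". That section adds only that change is the post-baseline score minus the baseline score.

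No section writes the formula or says which component is reversed.

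**The concern.** The two components run in opposite directions. A reader who takes the combination to be a plain sum finds that the direction statement fails: a patient at the worst end of both scales scores 85 + 0 = 85, a patient at the best end of both scores 0 + 56 = 56, and the maximum of 141 would need the worst cognition together with perfect function. On such a sum, a drug that helps cognition and function would show a smaller composite effect than it shows on cognition alone.

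The stated range does not settle the matter, because reversing either component also gives 0 to 141. If the cognitive score were the one reversed, higher would mean better, and a reader relying on Section 6.3.2.4 would take a benefit for a harm. The protocol writes out how the CDR-SB, FAQ, ADCS-iADL and NPI scores are summed (Sections 11.1.2 to 11.1.5). The iADRS, whose components have opposite signs, gets no such line.

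**Working it through.** **Range and direction.** Let A be ADAS-Cog13 (0 to 85, Section 6.3.1) and F be ADCS-iADL (0 to 56, Section 6.3.2.2). The stated maximum reproduces: 85 + 56 = 141. The best possible patient has A = 0, F = 56, and the worst has A = 85, F = 0.

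| Combination | Range | Best patient | Worst patient | Agrees with Section 6.3.2.4? |
|---|---|---|---|---|
| A + F | 0 to 141 | 56 | 85 | No: no consistent direction |
| A + (56 − F) | 0 to 141 | 0 | 141 | Yes: range, weights and direction |
| (85 − A) + F | 0 to 141 | 141 | 0 | Range and weights only; direction opposite |

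All three use unit weights and all give the stated range. The direction statement separates them, and it leaves one.

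**What the two reversals have in common.** (85 − A) + F = 141 − [A + (56 − F)]. Changes from baseline under the two are therefore exact negatives of each other. The treatment difference changes sign, while its standard error, two-sided p-value, power and confidence-interval width stay the same.

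**Size of the offset if raw scores were added.** The inputs are the 104-week planning differences (SD) in Section 12.3.1: ADAS-Cog 3.83 (13.54) in mild AD and 2.24 (12.96) in MCI; ADCS-iADL 2.85 (13.08) in mild AD and 0.41 (11.19) in MCI. The mix is 65% mild AD and 35% MCI (note to Table 7). The inputs reproduce the protocol's effect sizes: 3.83/13.54 = 0.28, 2.85/13.08 = 0.22, 2.24/12.96 = 0.17, 0.41/11.19 = 0.04.

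Benefit lowers A and raises F. The aligned effect is the sum of the two differences, and the raw-sum effect is ADAS-Cog minus iADL:

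- Mild AD: 3.83 + 2.85 = 6.68 against 3.83 − 2.85 = 0.98 (15% kept).
- MCI: 2.24 + 0.41 = 2.65 against 2.24 − 0.41 = 1.83 (69% kept).
- Mix: ADAS-Cog 0.65 × 3.83 + 0.35 × 2.24 = 3.27; iADL 0.65 × 2.85 + 0.35 × 0.41 = 2.00. Unrounded, 5.27 against 1.28 (24% kept).

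**Power under the same error.** Take 734 per arm and two-sided alpha 0.025. Effects are multiplied by 0.85, which is 0.70 + 0.30 × 0.5: the 30% dropout of Section 12.3.2.3 with the half effect in non-completers of Section 12.3.1. The SDs, weighted 65/35, are 0.65 × 13.54 + 0.35 × 12.96 = 13.3 and 0.65 × 13.08 + 0.35 × 11.19 = 12.4. The correlation between the two raw changes is not in the protocol; a range of −0.3 to −0.6 is assumed. Power per dose is then about 93 to 97% for the aligned score and about 19 to 33% for the raw sum.

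These losses arise only if someone programs the first row of the table, which the direction statement rules out.

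**The case for a change.** The strongest argument for a change is that the protocol does more than leave a formula to the SAP. It asserts a range and a direction, has a section meant to derive the score, and still does not say which component is reversed. The ADCS-iADL score itself is derived in Section 11.1.4 as a plain sum of 17 items with no reversal, so a programmer could add the two stored scores. A SAP that reversed ADAS-Cog13 instead would contradict Section 6.3.2.4. One sentence would remove the doubt.

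Three parts of this stand: the components run in opposite directions, the reversal is unwritten, and the range alone does not identify the formula.

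The step from there to a faulty composite does not stand. A linear combination may carry a coefficient of −1 and a constant, and excluding extra item weights does not exclude reverse scoring. Section 11.1.4 derives the stand-alone functional endpoint and does not govern the composite. Section 6.3.2.4 also describes the score as an overall measure of impairment that captures progression and treatment effects, which a raw sum would not be. The offset is therefore the result of a reading that the text contradicts, and even then it is partial and uneven: 85% of the aligned effect lost in mild AD, 31% in MCI.

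The opposite reversal carries a smaller risk, that of labelling the favourable direction wrongly. ADAS-Cog13 and ADCS-iADL are endpoints in their own right, so a composite pointing against both would be noticed.

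**Conclusion.** No change to the plan follows. Read as a whole, Section 6.3.2.4 is met by one unit-weight score, ADAS-Cog13 + (56 − ADCS-iADL), and that score is sound: 0 for the best patient, 141 for the worst, with cognitive and functional benefit counted in the same direction. The fall from 6.68 to 0.98 points in mild AD (5.27 to 1.28 in the mix) and the power of about 19 to 33% describe a sum that the protocol does not specify. Choosing the other reversal would change the sign and nothing else in a two-sided test.

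The missing formula is a detail that a SAP commonly supplies and that an analyst would fill sensibly from the stated range and direction. The primary endpoint and the sample size, both based on ADAS-Cog13 (Sections 12.2.4.1 and 12.3.1), are untouched.

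Two limits apply. The SAP was not available, so whether it writes the formula is unknown. The publication that the protocol cites for the scale was not available either, so whether its orientation agrees with the direction statement could not be checked. If it differs, the consequence is a wrong label for the favourable direction, not a loss of effect or power.

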6.3.2.5. Mini-Mental State Examination

The MMSE (Folstein et al 1975) is a brief test used to screen for cognitive impairment. It is routinely used for estimating the severity of cognitive impairment and tracking cognitive changes in an individual over time. The MMSE assesses orientation to time and place, immediate and delayed recall of words, attention and calculation, language (naming, comprehension and repetition), and spatial ability (copying a figure). The maximum total score is 30, with a higher score indicating better cognitive performance. The range of permissible scores at screening for enrollment of patients is 20 to 30, inclusive.

The MMSE assessment results will be recorded on worksheets. Administration of the MMSE will be audio-recorded for quality-control and training purposes where permitted by local law. Item-level scores from the worksheet will be transcribed into the eCRF. A sample of the MMSE worksheets and audio recordings will be centrally reviewed and monitored where permitted by

local law. Follow-up with raters will occur if concerns about administration and/or scoring practices are observed in central monitoring.

6.3.2.6. Neuropsychiatric Inventory

The Neuropsychiatric Inventory (NPI) is a well-validated clinical rating instrument designed specifically to assess a wide range of abnormal behaviors encountered in dementia patients (Cummings 1997, Cummings et al 1994). The NPI is an informant-based interview that utilizes scripted questions to explore 12 different symptom domains: delusions, hallucinations, agitation/aggression, dysphoria, anxiety, euphoria, apathy, disinhibition, irritability/lability, aberrant motor activity, night-time behavioral disturbances, and appetite and eating abnormalities. For each domain, the study partner is asked a screening question to determine whether the abnormal behavior has been present within the previous 4 weeks and represents a change in the patient since the onset of illness. If the behavior has been present, then a series of sub-questions are asked to obtain more detailed information about the specific features of the behavioral disturbance. For any behavior that has been present in the past 4 weeks, the study partner is asked to rate the frequency of the behavior on a 4-point scale (Rarely – less than once per week, Sometimes – about once per week, Often – several times per week but less than every day, Very often – once or more per day or continuously present), and the severity of the behavior on a 3-point scale (Mild – produces little distress in the patient, Moderate – more disturbing to the patient but can be redirected by the caregiver, Severe – very disturbing to the patient and difficult to redirect). A total score for each symptom is calculated by multiplying the frequency rating by the severity rating. The total NPI score is the sum of all symptom scores and has a possible range of 0 to 144, with higher scores indicating a greater degree of symptomatology.

The NPI also contains a Caregiver Distress Scale (NPI-D) that was designed to quantitate the distress experienced by caregivers as it relates specifically to the individual symptoms assessed in the patient by the NPI. For each symptom deemed to be present in the past 4 weeks, the study partner is asked to rate the distress the symptom has caused him or her on a 6-point scale (based on response to the question "How emotionally distressing do you find this behavior?"): 0 = not at all, 1 = minimally, 2 = mildly, 3 = moderately, 4 = severely, 5 = very severely or extremely. The maximum score for the Caregiver Distress Scale is 60.

The NPI assessment results will be recorded on worksheets, and item-level scores will be transcribed into the eCRF.

6.3.3. Exploratory efficacy variables

Exploratory efficacy variables in this study are the changes from screening/baseline that include but are not limited to: the Letter Fluency, Category Fluency, and Digit Symbol-Coding test scores, the NPI-D score, as well as the changes from screening in the RBANS score.

6.3.3.1. Letter Fluency, Category Fluency, and Digit Symbol-Coding tests

The Letter Fluency test is a measure of phonemic verbal fluency and executive functioning. The test consists of 3 trials. For each trial, the patient is asked to name as many words that start with a specific letter as he/she can in 60 seconds. Each trial is scored for the number of words

correctly generated and number of errors. The total number of correct words and total errors are derived by summing the scores across the 3 trials.

The Category Fluency test is a measure of semantic verbal fluency and executive functioning. The patient is asked to name as many animals as he/she can in 60 seconds. The test yields scores for the number of correct animal names generated and the number of errors.

The Digit Symbol-Coding test from the Wechsler Adult Intelligence Scale-III (Wechsler 1997) engages multiple cognitive abilities, including attention, psychomotor speed, complex scanning, visual tracking, and immediate memory. The test instrument is composed of 140 small blank squares presented in 7 rows. Each blank square is randomly paired with a number (1 to 9) printed directly above it. A key printed above the rows of blank squares pairs each number with an unfamiliar symbol. After completing 7 practice items, the patient must use the key to fill in the blank squares in order (working left to right across the rows) with the symbol that is paired with the number above it, working as quickly as possible within the time limit of 90 seconds. The test score is the number of blank squares filled in correctly within the time limit.

The Letter Fluency, Category Fluency, and Digit Symbol-Coding assessment results will be recorded on worksheets. Item-level scores from the worksheets will be transcribed into the eCRF.

6.3.3.2. Repeatable Battery for the Assessment of Neuropsychological Status

The RBANS is a collection of 12 subtests representing 5 neurocognitive domains: Immediate Memory, Visuospatial/Constructional, Language, Attention, and Delayed Memory. The RBANS administration generally requires 20 to 30 minutes.

The raw scores from each subtest within a domain are converted to a summary score, or Index Score, for the domain by consulting normative data tables. The RBANS also provides an overall Index Score that summarizes the patient's overall level of performance on this measure.

A Delayed Memory Index score of ≤85 at screening (Visit 1) is required for study eligibility.

The RBANS assessment results will be recorded on worksheets. Administration of the RBANS will be audio-recorded for quality-control and training purposes where permitted by local law. Subtest scores and Index scores from the worksheet will be transcribed into the eCRF. A sample of the worksheets for these assessments and audio recordings will be centrally reviewed and monitored where permitted by local law. Follow-up with raters will occur if concerns about administration and/or scoring practices are observed in central monitoring.

6.3.4. Order of efficacy assessments and rater qualifications

6.3.4.1. Order of efficacy assessments

The screening cognitive scales in Visit 1 should be administered before performing any imaging.

Assessments administered to the patient are the MMSE; RBANS; ADAS-Cog₁₃; Letter Fluency, Category Fluency, and Digit Symbol-Coding tests; EQ-5D-5L; and CDR. Assessments administered to the study partner include the FAQ, ADCS-ADL, CDR, NPI, and RUD-Lite.

Refer to Table 4 for the relative sequencing of tests for both patient and study partner. It is recommended that efficacy assessments be performed as the first activity at the baseline and subsequent visits. Additionally, it is recommended that, during these visits, cognitive and functional tests are performed in the sequence shown in Table 4. The CDR should always be administered to the study partner first and then to the patient; the study partner and patient must be interviewed separately.

It is important to maintain the same test sequence at each visit for each patient throughout the study. Assessments should be scheduled to allow the cognitive testing to be performed at approximately the same time of the day at all the visits to avoid the known circadian variation of cognitive performance (Higuchi et al 2000).

It is strongly recommended that patients and study partners be assessed separately, because the presence of the other person may potentially contaminate the results of an assessment. When necessary, patients should be allowed a rest break between cognitive tests. Based on rater judgment, other non-stressful study procedures may be conducted during these breaks.

Where there are multiple raters, ie, a psychometric rater and a global rater, the recommended sequence of tests allows for simultaneous testing. Table 4 describes the testing flow and respective rater responsibilities in this situation.

Table 4. Order of Test Administration for Patient and Study Partner and Rater Responsibilities

	Psychometric rater	Global rater
	Patient	Study partner
1)	MMSE	
2)	RBANS	1) FAQ
3)	ADAS-Cog ₁₃	2) ADCS-ADL
4)	Letter & Category Fluency tests	3) CDRa
5)	Digit Symbol-Coding test	
6)	EQ-5D-5L	
	Study partner	Patient
4)	NPI	7) CDRa
5)	RUD-Lite	

All tests may not be administered at each visit; the relative order of tests is maintained for any tests that are administered at the same visit.

Abbreviations: ADAS-Cog₁₃ 13-item Alzheimer's Disease Assessment Scale - Cognitive subscale; ADCS-ADL The Alzheimer's Disease Cooperative Study Activities of Daily Living Inventory; CDR Clinical Dementia Rating; FAQ Functional Activities Questionnaire; MMSE Mini-mental State Examination; NPI Neuropsychiatric Inventory; RBANS Repeatable Battery for the Assessment of Neuropsychological Status; RUD Resource Utilization in Dementia.

